4.7. Co-enrollment Criteria

HIV-positive patients who include into this study are still permitted to follow other observational studies as participants. However, patients who participate in this study are not permitted to take other interventional studies. Sticker affixed in participant's medical record as required by hospital policy will ensure that participant is not under other interventional study.

4.8. Study Instruments

Instruments used in this study included an ICF, demographic form contains medical record and essential information of each participant, CIMT examination form, blood collection and sample storage form, adherence form. A paper based forms that will be transferred to electronic format.

4.9. Strategies for Recruitment

Potential subjects as participants in this study are all adult patients who meet the eligible criteria and under antiretroviral therapy at HIV Integrated Care Unit Cipto Mangunkusumo Hospital. These patients regularly control once for each two or a month(s) but antiretroviral drugs be refilled monthly. A promotion poster will be placed in the clinic area during the enrollment period.

4.10. Participant Retention

To enhance participant retention, all participant will be monitored by research assistant using phone once every two weeks. In addition, a reminder of the next schedule visit will be sent a week before.

4.11. Study Intervention

4.11.1. Study drug and dosage:

- Atorvastatin 20 mg tablets in generic form
- The placebo tablets will be prepared by Cipto Mangunkusumo hospital pharmacist, were composed of starch and were similar to atorvastatin tablets in size, shape, and colour.

4.11.2. Treatment administration:

The administration of study drug is home-based participant self-administration. The participants will get the medication after randomization process (week – 0) at least 1 week after. The participants will get supply every month along with the refill of antiretroviral drugs. The drug and placebo tablets will be administered to patients by a staff member who are privy to the treatment. In the end of every month, each participant should return the unused pills every month. All prescriptions will use hospital Electronic Medical Record system.

4.11.3. Drug interaction:

During this study, each participant is not allowed to use cyclosporin, fenofibrate, and rice yeast herbal supplements.

4.12. Intervention Assignment Procedures

4.12.1. Randomization Procedures

Research assistant will do randomization for each participant using computerized statistic application.

4.12.2. Masking Procedures

Study pharmacist will make code (A and B) for atorvastatin and placebo, then save the code in safe place. Pharmacist will record each subject as participant received A or B intervention.

Patients, managing doctor, researcher, and those assessing outcomes would not know what type of drug given. The code will only be opened when a participant having adverse event that require identification of study drug, ie drug allergy and acute coronary syndrome.

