4.2. Study Plan

4.3. Study Design

This study used a double-blind randomized placebo-controlled trial design. Participants who met the inclusion and exclusion criteria were randomized into atorvastatin groups and placebo groups with a ratio of 1: 1 (40 subjects per group). Randomization using a computer program based on randomization of permutation blocks with block 4 sizes carried out by statistical analysts. Then the code is given to pharmacists who involved in the study. Researchers, doctors, and participants did not know the results of randomization.

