4.13.2. Baseline and Enrollment

Subjects with undetectable HIV-RNA, positive anti-CMV, having Framingham Risk Score above 10% with LDL < 130 or under 10% with LDL <160 will undergo thorough medical history and anthropometric examination as the initial data. Venous blood sample will be collected for fasting blood glucose, ALT, CMV DNA, hsCRP, sCD14, VCAM, ICAM, and β 2M examinations. CIMT, transient elastography with CAP, neurocognitive function, and community periodontal index procedure will be done within a week before taking study drugs. CIMT and FMD evaluation will be done by trained cardiologist using B mode ultrasonography. Transient elastography with CAP will be done by trained cardiologist Fibroscan (Echosens) device. A trained neurologist will do neurocognitive evaluation using trail making test (TMT) A and TMT B (attention and executive function), digit symbol (processing speed), brief visuospatial memory test revised (visual and visuospatial memory), and California verbal making test (verbal memory).

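### With one A/B key shared by all 80 participants, unmasking one of them can decode the other 79 to anyone who knows their letters

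*Combined protocol and SAP*

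**What the plan says.** Section 4.12.2 (Masking Procedures) describes one code with two values: "Study pharmacist will make code (A and B) for atorvastatin and placebo, then save the code in safe place". Participants are tied to it by letter: "Pharmacist will record each subject as participant received A or B intervention". The code is to "only be opened when a participant having adverse event that require identification of study drug, ie drug allergy and acute coronary syndrome".

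The intended masking is broad. Section 4.12.2 says "Patients, managing doctor, researcher, and those assessing outcomes would not know what type of drug given", and section 4.3 adds "Researchers, doctors, and participants did not know the results of randomization".

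Several roles handle the allocation. Section 4.3 has "randomization of permutation blocks with block 4 sizes carried out by statistical analysts", with the code then passed to the pharmacists. Section 4.12.1 says "Research assistant will do randomization for each participant using computerized statistic application". Section 4.11.2 has study drug handed out by a staff member who knows the treatment.

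The protocol describes no participant-level treatment number and no individual code break. It does not limit a disclosure to the affected participant, name its recipient or require a log.

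**The concern.** The code break is triggered by one participant's event, but what is opened is a key common to everyone. With two letters, knowing one gives the other by elimination. Anyone who learns what a letter means, and who knows which letter other participants carry, then knows those participants' arms.

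The stake is masked outcome reading. The primary endpoint is the CIMT change from baseline to week 48, and section 4.13.2 says "CIMT and FMD evaluation will be done by trained cardiologist using B mode ultrasonography". Under section 4.13.3, CIMT, flow-mediated dilatation (FMD), elastography, neurocognitive and periodontal assessments are all repeated at week 48. Masking therefore has to survive any code break during the preceding year. Under a shared key, it survives only if those who hear the result cannot connect it to a letter, or do not know the other participants' letters. The protocol secures neither condition.

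**Working it through.** **Number of participants.** Section 4.5 gives a difference of 0.1, SD 0.12, 90% power and a 5% level (two-sided assumed, as the section does not say). The exact two-sample t-test solution is 31.25, so 32 per arm. Allowing for 20% dropout gives 32 / (1 − 0.20) = 40 per arm, or 2 × 40 = 80 in total. The plan's figures reproduce, and section 4.3 also gives 40 per group.

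**Shared A/B key, one letter's meaning disclosed, full 40:40 enrolment.**
- Others on the same letter: 40 − 1 = 39.
- Others on the other letter: 40.
- Total decoded: 39 + 40 = 79 of 80, for someone who knows all the letters.
- Total decoded: 0, for someone who knows no letters.

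The figure of 79 is the maximum. A break before accrual ends would expose those already enrolled, and later entrants as they join.

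**Participant-level numbers, one participant's drug disclosed.**
- Others decoded directly: 0 of 79.
- Residual information from blocking: a block of 4 at 1:1 has 6 possible orders. If one participant is known to be on atorvastatin, 3 orders remain, and each of the 3 block-mates is on placebo in 2 of those 3. A guess of the opposite arm is then right with probability 2/3 instead of 1/2, but only for someone who knows the block size and the allocation order.
- Outside that block: 80 − 4 = 76 participants stay at 1/2.

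**Who could know the letters.** The protocol does not say whether letters appear on labels, prescriptions or case report forms. The places that bear on it are:
- Section 4.3: the statistical analysts produce the allocation. Section 6.1 has the analyst also build the study database, which the research team keeps.
- Section 4.12.1: a research assistant carries out randomisation. Section 4.10 has a research assistant phone participants every two weeks.
- Section 9.6: researchers, the pharmacist and the analyst have access to the files, with no exception written for the pharmacist's A/B record.

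None of these shows that a masked person sees letters. Equally, none establishes that letters stay in pharmacy.

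No code-break probability, bias or type I error is calculated, because the documents give no event rate, leak probability or reading bias.

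**The case against.** The strongest reply is that the scheme can be run safely as written. The pharmacist holds both the key and the record, and can say which drug one participant received without mentioning a letter. The stated intent is that doctors, researchers and assessors stay masked, and opening the code can be read as looking up one participant. This stands in part: nothing in the documents shows that a break would spread. But reporting only the drug protects only against people who do not know that participant's letter. For someone who does, drug plus letter gives the key. The safeguard that counts is that letters never leave pharmacy, and that is not written.

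Breaks may also be rare. Participants are aged 20 to 45, and a history of coronary artery disease or statin hypersensitivity is excluded. That is fair, and it is one reason no probability is attached. It does not remove the weakness, because section 4.12.2 itself provides for breaks.

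The dispenser in section 4.11.2 knows the treatment under either scheme, so individual codes do not remove every source of arm knowledge. This stands: the change closes the code-break route only.

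Finally, one sentence could suffice: the pharmacist tells the treating doctor the drug, without the letter, and logs it. That would be an improvement, but masking of the other 79 would still rest on the letters staying unknown.

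**Conclusion.** The concern holds. Section 4.12.2 ties all 80 participants to one two-letter key and opens that key for a single participant's event. One disclosed letter decodes up to 79 others to anyone who knows their letters, against none directly with participant-level codes. The 79 assumes full 40:40 enrolment and knowledge of every letter.

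Trial-wide unmasking is a possibility that the design leaves open; the documents do not show that it would happen. Sample size and power are unaffected. This is a weakness that should be corrected, because the primary endpoint depends on masked measurement and the correction is cheap. Confidence is medium, since the practical risk turns on who sees the letters, which the protocol does not state.

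**What to change.** In section 4.12.2:
- Replace the A/B key with a unique treatment number for each participant, linked to the randomisation list held by the pharmacist.
- Keep one sealed code break per participant, so that opening it shows only that participant's drug.
- State that the result goes only to the treating doctor, and not to the CIMT/FMD, neurocognitive or other outcome assessors.
- Require each break to be logged.

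The cost is 80 sealed code breaks, and monthly packs labelled by participant number (about 12 × 80 = 960). Drug is already dispensed monthly under section 4.11.2, so no extra visits, tests or participants are needed. The small residual for block-mates in the working remains.

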4.13. Study Schedule and Procedures

Each participant will be followed for one year after start using study drug.

4.13.1. Screening

Patients meeting the initial screening criteria will be test for HIV RNA (viral load), anti-CMV and fasting lipid profile:

- Age between 20 to 45 years old
- Using ART at least 1 year
- Not under hepatitis C therapy
- No history of coronary artery disease, brain infection, epilepsy, stroke
- No diabetes mellitus
- Not pregnant or breastfeeding
- Not severe depression (using mini ICD10)
- Not using statin therapy

4.13.2. Baseline and Enrollment

Subjects with undetectable HIV-RNA, positive anti-CMV, having Framingham Risk Score above 10% with LDL < 130 or under 10% with LDL <160 will undergo thorough medical history and anthropometric examination as the initial data. Venous blood sample will be collected for fasting blood glucose, ALT, CMV DNA, hsCRP, sCD14, VCAM, ICAM, and β 2M examinations. CIMT, transient elastography with CAP, neurocognitive function, and community periodontal index procedure will be done within a week before taking study drugs. CIMT and FMD evaluation will be done by trained cardiologist using B mode ultrasonography. Transient elastography with CAP will be done by trained cardiologist Fibroscan (Echosens) device. A trained neurologist will do neurocognitive evaluation using trail making test (TMT) A and TMT B (attention and executive function), digit symbol (processing speed), brief visuospatial memory test revised (visual and visuospatial memory), and California verbal making test (verbal memory).

4.13.3. Follow Up Visit(s)

Patient will be seen for regular clinical follow up as standard of care in the clinic (monthly/ bimonthly). Follow up visit will include clinical and laboratory procedure as presented in table study schedule (appendix).

At week 24, blood collection procedures and neurocognitive examination procedures will be repeated. At week 48, blood collection procedures, CIMT, FMD, transient elastography with CAP, neurocognitive examination, and community periodontal index procedures will be repeated.

4.13.4. Other visit

Other visit or investigations (or referral to other clinical specialists) may be requested as clinically indicated. These include side effect encountered and other treatment related issue.

4.13.5. End of Study Visit

In the end of study (week 48), a total drug consumption adherence will be assessed using Medication Possession Ratio (MPR) method.

5. SPECIMENS (REPOSITORY, USAGE, LOSS & DESTRUCTION)

5.1. Biohazard Containment

This study using a blood samples which will be analyzed by laboratory analysis. So, that will increase the risk of infection for laboratory analysis.

5.2. Specimen Preparation, Handling, Storage and Shipping

Before a blood sample collection, the subject is required to fasting minimum 8-10 hours. Blood glucose, lipid profile, IgG anti-CMV, ALT, and viral load will be checked at the time in hospital laboratory service. For other evaluation, the blood sample will be inserted into a tube with EDTA preservative and will be centrifuged to become plasma. Then, the plasma will be aliquoted into several tubes and will be saved in -80°C refrigerator.

5.3. Total Blood Volume

Subjects who are willing to take this part in this study will take maximum 12 mL of venous blood sample in each visit (see appendix).

6. DATA MANAGEMENT, STATISTICAL CONSIDERATION & ANALYSIS PLAN

6.1. Data Management

Data management will be managed in HIV Integrated Care Unit, Cipto Mangunkusumo Hospital.

- a. Specific Case Report Forms (CRF) will be created prior to study
- b. A study-specific, relational electronic database will be created to house the anonymized study data by statistical analyst and saved by research team.
- c. Prior to patient recruitment and data collection, all research team will receive training in study procedures.

All research team will have overall responsibility for maintaining the study CRFs. Corrections to the paper CRF documents must be made by striking through the incorrect entry with a single line (taking care not to obliterate or render the original entry illegible) and entering the correct information adjacent to the incorrect entry. Corrections to paper CRFs must be initialed and dated by the person making the correction. The researchers are responsible for maintaining accurate, complete and up-to-date records. These forms are to be completed on an on-going basis during the course of the study.

6.2. Statistical Consideration & Analysis Plan

Subjects will be analyzed in the group to which they were randomized, regardless of the treatment received.

6.2.1. Analysis of primary endpoints

T test will be used to compare the mean CIMT changes of virally suppressed HIV patients with CMV seropositivity in atorvastatin group versus placebo group between baseline and week 48.

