3.2. Secondary endpoints

1. Magnitude of change in effect of atorvastatin on CIMT associated with baseline CMV copy number
2. The mean or median changes of fasted lipid between baseline and week 24, week 24 and week 48

3. The mean or median changes of brachial artery flow mediated vasodilatation (FMD) between baseline and week 48
4. The mean or median changes of liver fibrosis and steatosis in atorvastatin and placebo group between baseline and week 48
5. The mean or median changes of sCD14, VCAM, ICAM, CRP, and β 2M in atorvastatin and placebo group lipid between baseline and week 24, week 24 and week 48
6. The mean or median changes of neurocognitive function in atorvastatin and placebo group lipid between baseline and week 24, week 24 and week 48
7. The mean or median changes of oral periodontitis score in atorvastatin and placebo group between baseline and week 48
8. Magnitude of change in effect of atorvastatin on FMD, neurocognitive function, liver fibrosis and steatosis, lipid profile, and immune activation biomarkers associated with baseline CMV copy number

[figure not shown]

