4.5. Population and Sample Size

Target population is HIV-positive patient on stable ART routinely controlled in HIV Integrated Care Unit Cipto Mangunkusumo Hospital, Jakarta.

Assuming that the effect size is 0.1, standard deviation is 0.12, and the use of 2 sample t-test, the sample size needed for 90% power and 5% significant level is 32 per arm. With additional 20% drop, each arm (placebo and control group) will need 40 participants.

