6.2.2. Analysis of secondary endpoints

- Linear regression with interaction will be used to assess magnitude of change in effect of atorvastatin on CIMT associated with baseline CMV copy number
- For other continuous endpoints, a 2 sample T-test

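### The primary t-test on CIMT change is valid, but pre-specifying baseline CIMT as a covariate would add precision at almost no cost

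*Combined protocol and SAP*

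**What the plan says.** Section 6.2.1 gives the whole primary analysis in one sentence: a "T test will be used to compare the mean CIMT changes of virally suppressed HIV patients" between the atorvastatin and placebo arms, from baseline to week 48. Section 6.2.2 extends this: "For other continuous endpoints, a 2 sample T-test". The only regression in the plan is the secondary model for the interaction with CMV copy number, and it does not name baseline CIMT.

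The sample size in section 4.5 rests on the same test: "Assuming that the effect size is 0.1, standard deviation is 0.12, and the use of 2 sample t-test". It concludes that "the sample size needed for 90% power and 5% significant level is 32 per arm", raised to 40 per arm for 20% dropout. It does not say whether 0.12 is the SD of the change or of a single CIMT measurement. Appendix B defines CIMT change in millimetres.

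Baseline CIMT is available. Section 4.13.2 lists it first among the examinations for which it says "community periodontal index procedure will be done within a week before taking study drugs", and Appendix A places it at visit 0. Section 4.3 describes permuted blocks of 4 and names no stratification factor.

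**The concern.** A change score uses the baseline value, but forces its coefficient to be exactly 1. When baseline and week-48 values are imperfectly correlated, that over-corrects: part of the noise in the baseline measurement is carried into the estimate. Regression on arm and baseline lets the data set the coefficient and estimates the same mean difference between arms.

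Two things are at stake in a trial of 80 people with one primary comparison. The first is the width of the confidence interval. The second is how a chance difference in baseline CIMT will be handled. Nothing in the randomisation balances CIMT, so such a difference may well appear in the baseline table. An adjustment chosen after seeing it is open to challenge; one fixed beforehand is not.

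**Working it through.** **Inputs.** From section 4.5: difference 0.1 (taken as mm, following Appendix B), SD 0.12, 5% level, 90% power, 32 per arm. Assumed, because the documents do not give them: the correlation r between baseline and week-48 CIMT, shown over a range, and equal variances at the two visits.

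**The plan's own figure.** The normal approximation gives 2 × (1.960 + 1.282)² × 0.12² / 0.1² = 30.3, so 31 per arm. The exact two-sided t-test (noncentral t) has power 89.8% at 31 and 90.7% at 32, so 32 per arm is reproduced. Then 32 / 0.8 = 40.

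**Formulas.** With SD s of a single measurement:

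- SD of change = s√(2(1−r))
- residual SD after adjustment = s√(1−r²) = SD of change × √((1+r)/2)
- variance ratio, adjusted to unadjusted = (1+r)/2, multiplied by 1 + 1/60 for estimating the slope with 32 per arm
- 95% CI half-width = t × SE, where SE is SD × √(2/32) = SD/4, with the adjusted SE also multiplied by √(1 + 1/60); degrees of freedom are 62 unadjusted and 61 adjusted
- effect on the unadjusted estimate of a baseline imbalance of one standard error = (1−r) × s × √(2/32)

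All adjusted figures below include the cost of estimating the slope.

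**Reading A: 0.12 is the SD of change.** Unadjusted power is 90.7% and half-width 0.060 mm whatever r is.

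| r | Residual SD | Variance ratio | Adjusted power | Adjusted half-width (mm) | 1-SE imbalance shift, unadjusted (mm) |
|---|---|---|---|---|---|
| 0.5 | 0.1039 | 0.76 | 96.4% | 0.052 | 0.015 |
| 0.7 | 0.1106 | 0.86 | 94.2% | 0.056 | 0.012 |
| 0.9 | 0.1170 | 0.97 | 91.6% | 0.059 | 0.007 |

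Break-even is where (1+r)/2 × (1 + 1/60) = 1, that is r ≈ 0.97.

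**Reading B: 0.12 is the SD of a single measurement.**

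| r | SD of change | Residual SD | Power, t-test | Power, adjusted | Half-width, t-test → adjusted (mm) |
|---|---|---|---|---|---|
| 0.3 | 0.1420 | 0.1145 | 79.2% | 92.7% | 0.071 → 0.058 |
| 0.5 | 0.1200 | 0.1039 | 90.7% | 96.4% | 0.060 → 0.052 |
| 0.7 | 0.0930 | 0.0857 | 98.9% | 99.5% | 0.046 → 0.043 |
| 0.9 | 0.0537 | 0.0523 | >99.9% | >99.9% | 0.027 → 0.026 |

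**Simulation check** (Reading A, 20,000 trials per setting, slope estimated, r = 0.5, 0.7, 0.9). Under no effect, both tests reject in 4.8–4.9% of trials. Under 0.1 mm, adjusted power is 96.3%, 94.2% and 91.6%, against about 91% unadjusted. Simulated variance ratios are 0.76, 0.86–0.87 and 0.96–0.97, as the formula predicts.

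**The case against.** The strongest reply is that nothing is broken. Objective, endpoint, sample size and test form a consistent chain, and the trial meets its 90% target under its own assumptions. This is accepted: the point concerns efficiency.

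A second reply is that carotid thickness may track so closely over 48 weeks that the gain disappears. At r = 0.9 the half-width moves by only 0.001 mm. That also stands, but the documents give no r, and the choice is lopsided: about 24% less variance at r = 0.5 against a trivial loss beyond about 0.97.

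Third, the most striking contrast, 79.2% against 92.7%, needs both r = 0.3 and the reading of 0.12 as the SD of a single measurement. Since section 6.2.1 applies the test to changes, SD of change is the more natural reading. The case should rest on Reading A, with Reading B as a reason to clarify section 4.5.

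Fourth, protection against baseline imbalance is not a separate benefit. The variance saved is 2(1−r)s² − (1−r²)s² = (1−r)²s², which is exactly the imbalance component. The t-test's standard error already contains it, so it is not bias. This is correct: the imbalance shifts are the same gain seen conditionally on the baseline actually observed.

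Finally, the gain is worked out for CIMT only, and the t-tests on week 24 to week 48 changes are not at fault as written. Both are true. The secondary endpoints matter because, once adjustment is introduced, the wrong covariate could be used for those intervals. Endpoints such as "The mean or median changes of fasted lipid between baseline and week 24, week 24 and week 48" include an interval whose starting value is already affected by treatment.

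**Conclusion.** The point holds as a recommended improvement. The t-test is valid and 32 per arm is right for it. Adding baseline CIMT estimates the same quantity, keeps the 5% level and, if 0.12 is the SD of change, lowers the variance by about 24% at r = 0.5, 14% at r = 0.7 and 3% at r = 0.9. The direction is secure for any r below about 0.97. The size is not, because it rests on an assumed r, on equal variances at the two visits and on which SD section 4.5 means.

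**What to change.** **Section 6.2.1.** Replace the sentence with: *Week-48 CIMT (equivalently, change in CIMT) will be compared between arms by linear regression on arm and baseline CIMT measured before study drug, at the two-sided 5% level, reporting the adjusted mean difference and 95% CI. The two-sample t-test on change is a sensitivity analysis.*

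**Section 6.2.2.** For continuous endpoints measured as change from baseline to week 24 or week 48, use the same model with that endpoint's pre-drug value as covariate. For lipids this is the screening value, since Appendix A shows no lipid profile at randomisation. For week 24 to week 48 changes, regress the change on arm and the pre-drug value only; do not use the week-24 value as a covariate.

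**Section 4.5.** State whether 0.12 is the SD of change or of a single measurement.

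The cost is two edited paragraphs, one clarifying phrase and one degree of freedom, with about 1.7% variance inflation (1/60) for estimating the slope. No new data are needed and the planned 40 per arm need not change. The text should be fixed before unblinding.
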